4.3 STUDY VISIT PROCEDURES

Participants will arrive to the lab at 9 AM fasted overnight prior to the alcohol administration study visits. Identity will be confirmed by verification of photo ID and pregnancy will be confirmed with a urine pregnancy screen. Abstinence from alcohol will be confirmed with a breathalyzer. Mode of transportation to the session will be confirmed. Participants will be encouraged to arrange for a ride or take public transportation to sessions to minimize the risk of driving while intoxicated. In the case that a participant drives themselves to the session, the participant will be required to sign an acknowledgment that their keys will be held by the research assistant during the session and returned after the subject's BAC reaches zero. Blood will be sampled with venipuncture to analyze baseline plasma GLP-1. Fingerprick blood sample will be used to measure HMGB1. Baseline measurements of study outcomes will be taken at this time. Participant will complete additional baseline measures at home including: demographics form, the Alcohol Use Disorder Identification Test (AUDIT) [57], Obsessive Compulsive Drinking Scale (OCDS) [58], Reward-based Eating Drive Scale (RBEDS) [59], Body Perception Questionnaire (BPQ) [60], Drinking Motives Questionnaire (DMQ) [61], Comprehensive Relative Autonomy Index for Drinking (CRAI Drinking) [62], Alcohol Sensitivity Questionnaire (ASQ) [63], and the Impaired Control Scale (ICS) [64], and the Inventory of Drinking Situations (IDS) [65] using REDCap to explore potential moderators in secondary analyses. Assessments will occur in a study room furnished to feel like a comfortable living room with a TV. Participants may watch TV or engage in relaxing recreational activities (e.g. reading, personal computer) during recovery from alcohol. Participants will be fitted with a Skyn TAC wrist monitor and finger-tip sensor to monitor alcohol exposure and be trained on using the BACtrack S80 for BrAC measures. Participants will download the Skyn app to sync the Skyn data during the session, and then will be instructed to refrain from using their phones for non-study related purposes.

Dietary manipulation

Participants will receive a beverage containing either a dietary supplement (10g Fibersol®-2 mixed with water and aspartame sweetener for taste + 725mg decaffeinated green tea extract capsule) or a calorically matched placebo supplement (Aspartame sweetener mixed with water + aspartame capsule) counterbalanced at two separate visits. Forty-five minutes after the dietary supplement, the second blood sample is taken. Next, a priming drink (calculated to achieve 30mg% BAC) is administered to stimulate craving for alcohol [66, 67]. Drinks will consist of 40 proof vodka and a sugar-free cranberry juice mixer at a 1:5 ratio. Doses are calculated to achieve target BACs based on sex and body weight using formulas established in prior research [68]. Fifteen minutes after the priming drink, a novel alcohol-specific satiety questionnaire will be administered followed by alcohol incentive motivation tasks (alcohol purchase task; APT [69], dot probe attentional bias to alcohol-related stimuli), additional validated alcohol subjective response questionnaires (Drug Effects Questionnaire; DEQ[70], Biphasic Alcohol Effects Scale; BAES [71], Alcohol Urge Questionnaire; AUQ [72], Subjective Effects of Alcohol Scale; SEAS [73]), *hunger, fullness, and satiety* visual analogue scale (VAS) items, a BACtrack S80 BrAC measure, and a fingerprick blood sample.

Alcohol-specific satiety paced drinking procedure

Then over a 2-hour period, 5 additional mini-drinks (calculated to achieve an estimated BAC increase of 10mg% each or placebo) are administered with 15 min absorption time between each drink to reach an estimated maximum BAC of 60-70mg%, reflecting a moderate level of alcohol exposure (80mg% is the conventional cutoff for “binge” exposure). Participants have 3 minutes to finish each drink (Average volume of a drink, alcohol+mixer at a 1:5 ratio is 8/5oz for a man/woman). This paradigm is designed to approximate a natural drinking pace, while controlling for the BAC during subjective satiety assessment. The control session will control for expectations of increased satiety with subsequent drinks. Control drinks contain cranberry juice with an alcohol mask (rim sprayed with vodka) matched in total volume to the alcohol drinks. Participants will be told that all drinks contain alcohol. Subjective response questionnaires are repeated 15 minutes after each drink. BACtrack S80 BrAC measures are repeated every 15 minutes.

After the paced drinking procedure, a final fingerprick blood sample will be taken and participants will remain in the lab until their BAC reaches 0mg% at which point they will be either dismissed. At the end of the second lab session, participants will receive instructions on using the Skyn and BACtrack S80 devices, using the Skyn app for syncing Skyn data and the LifeData app for completing drinking bout EMA surveys and morning surveys about past day alcohol use and consequences.

Remote assessment

During the 7-day naturalistic study, participants will be asked to wear the Skyn for 24 hours/day for 7-days (except when bathing or swimming). On days when participants choose to drink they will initiate drinking bout surveys via smartphone by indicating they have started drinking, after which they will be prompted to provide a BrAC reading once every 20-minutes throughout the drinking bout and for up to 1-hour after the drinking bout ends. Every 60-minutes participants will also self-report alcohol amount and subjective intoxication during the drinking bout. Importantly, participants will be informed that they are not expected to change their drinking behaviors during the study and compensation is not contingent on self-reports or breathalyzer readings during drinking bouts. Participants will complete daily morning surveys about past day alcohol use and consequences and evening surveys about daily pain and stress.

After the 7-day protocol, participants will return their devices to the PI's lab and report past 7-day drinking behaviors (timeline follow-back; TLFB) and drinking consequences (Brief Young Adult Alcohol Consequences Questionnaire, Importance of Consequences of Drinking short-form) and undergo a DEXA scan. Participants will be compensated upon device return with up to \$240 (\$20 for baseline surveys, \$50 for lab visit one, \$50 for lab visit two, \$70 for all 7-day EMA study procedures, \$10 for device return, \$10 for follow-up questionnaires, \$10 for DEXA scan, and \$10 study completion bonus).

Blood sampling: Blood is sampled at baseline and again 45 minutes after dietary supplement administration to assess the effect of the dietary manipulation on circulating GLP-1. Blood samples will be immediately placed on dry ice and centrifuged the same day. Extracted plasma will be stored at -80° C. Blood samples will be collected in a 2mL vacutainer pretreated with a DPP-4 inhibitor in accordance with manufacturer guidelines (EMD Millipore Corp., Billerica, MA). Only biologically active forms of GLP-1 will be measured which include GLP-1(7–36) and GLP-1(7–37) [74]. Blood samples will be processed in duplicate with the MILLIPORE Glucagon-Like Peptide-1 (Active) ELISA kit - 96-Well Plate (Cat. #EGLP-35K). HMGB-1 will be measured at three timepoints via a fingerprick blood sample. Plasma samples will be processed in duplicate using a deproteinization kit and the HMGB1 ELISA kit - 96-Well Plate (Cat. # EEL047).

Dietary supplements: commercially available supplements will be used to stimulate glp-1; 10g prebiotic fiber (digestive resistant maltodextrin; fibersol®-2) and 725mg decaffeinated green tea extract (<https://www.vitaminshoppe.com/p/triple-strength-green-tea-extract-100-vegetarian-capsules/vs-1807>). Dietary fiber [54, 55, 75-77] and green tea extracts [78, 79] separately have been shown to increase plasma levels of active glp-1 in randomized controlled studies. These supplements will be used together for the purposes of this research aim, which prioritize efficacy of the glp-1 manipulation over an investigation of any particular supplement. Effective doses of each supplement have been chosen which have been shown to be safe and tolerable for human subject research in prior studies [52, 80, 81]. Aspartame (Equal®) was chosen as a placebo based on prior research indicating that non-nutritive sweeteners are unlikely to stimulate GLP-1 release [82, 83].

BACtrack Skyn TAC Monitor: The BACtrack Skyn is a small, lightweight wrist monitor that measures alcohol exposure through the 1% of alcohol transmitted through perspiration (i.e., transdermal alcohol concentration). The device wirelessly syncs to the Skyn app on the participant's iPhone to collect TAC data every 20 seconds. Alcohol exposure is detected with an average delay of 35.6 minutes [84]. The following outcomes are derived from TAC data: *drinking intensity* (peak TAC and area under the curve [AUC]), *drinking duration* (hours with TAC >0 µg/L air), *rise rate* (average rate of all ascending point-to-point TAC values), and *fall rate* (average rate of all descending point-to-point TAC values).

BACtrack S80 BrAC Monitor: The BACtrack S80 is a portable, battery-operated professional breathalyzer that measures the percentage of alcohol in a person's breath (i.e., BrAC). Participants capture BrAC within seconds after following a series of automated instructions provided by the S80 and breathing into the mouthpiece. Participants will report their S80 readings in the EMA surveys. The outcomes derived from the BrAC data are the same as those described above for TAC data.

Behavioral tasks:

The alcohol purchase task (APT) measures the hypothetical behavioral economic demand for alcohol at 14 different price points. This measure is sensitive to the reinforcing effects of alcohol, and predictive of real-world alcohol consumption [69]. The following outcomes are derived from the APT: APT-intensity (consumption when drinks were free); APT-breakpoint (the first price at which consumption was suppressed to zero); and APT-Omax (maximum alcohol expenditure) [69]. The task takes no more than 5 minutes to complete and is administered on REDCap

The dot probe is a measure of cognitive attentional bias used in prior studies thought to reflect the incentive salience of alcohol related stimuli [85, 86]. This task will be administered on E-Prime software. Subjects are sat at a computer and shown left-right pairs of images on a screen for 1000ms followed by a white dot in place of one of the images. Participants are instructed to respond to the dot probe target with a key using their left hand if the dot is on the left side, and the right hand if the target appears on the right side. Pairs of images include alcohol related images matched with control images (non-alcohol beverages such as soda, a glass of water, etc.). 10 image pairs are presented four times each for a total of 40 critical test trials. 40 additional trials are randomly interspersed with critical trials which feature neutral filler images (office supplies, etc.). The target may either be congruent to the alcohol-related stimuli (target appears on the same side as the alcohol-stimuli) or incongruent (target appears on the side of the control stimuli). The task takes 5 minutes to complete. Faster reaction times to alcohol-related imagery on congruent trials (alcohol image displayed on the same side as the dot probe target) and slower reaction times on incongruent trials reflect increased attentional bias towards the alcohol-related stimuli. Therefore, reaction time to alcohol cues > neutral cues on incongruent > congruent trials reflect the attentional bias score [86]. Attentional bias will be assessed before and after alcohol administration and change scores will be calculated.

List of Measures (See section 1.3 for assessment time points)

1. Demographics form
2. Alcohol Use Disorder Identification Test (AUDIT)
3. Inventory of Drinking Situations (IDS)
4. Obsessive Compulsive Drinking Scale (OCDS)
5. Reward-based Eating Drive Scale (RBEDS)
6. Body Perception Questionnaire (BPQ)
7. Drinking Motives Questionnaire (DMQ)
8. Comprehensive Relative Autonomy Index for Drinking (CRAI- D)
9. Alcohol Sensitivity Questionnaire (ASQ)
10. Impaired Control Scale (ICS)
11. Alcohol-specific satiety questionnaire
12. Drug Effects Questionnaire (DEQ)
13. Visual Analogue Scale items (VAS)
14. Biphasic Alcohol Effects Scale (BAES)
15. Subjective Effects of Alcohol Scale (SEAS)
16. Alcohol Urge Questionnaire (AUQ)

17. Alcohol Purchase Task (APT)
18. Dot Probe attentional bias to alcohol related cues task
19. Breath Alcohol Concentration (BrAC)
20. Transdermal Alcohol Concentration (TAC)
21. Ecological Momentary Assessment Questions (EMA)
22. Timeline followback
23. Brief Young Adult Alcohol Consequences Questionnaire
24. Importance of Consequences of Drinking short-form

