1.2 SCHEDULE OF ACTIVITIES (SOA)

Procedures	Online Prescreen	Virtual Visit	Study visit 1	Study Visit 2	7 day Remote Assessment	Discharge visit
Online prescreen survey	X					
Informed consent		X				
DSM-5 SCID AUD and SUD		X				
Demographics Form		X				
Alcohol Use Identification Test (AUDIT)		X				
Inventory of Drinking Situations (IDS)		X				
Obsessive Compulsive Drinking Scale (OCDS)		X				
Reward-based Eating Drive Scale (RBEDS)		X				
Body Perception Questionnaire (BPQ)		X				
Drinking Motives Questionnaire (DMQ)		X				
Comprehensive Relative Autonomy Index for Drinking (CRAI Drinking)		X				
Alcohol Sensitivity Questionnaire (ASQ)		X				
Impaired Control Scale (ICS)		X				
Dietary supplement or placebo			X	X		
Administer alcohol priming drink			X	X		
Paced alcohol or control drinking			X	X		
Weight and height			X			
Pregnancy test			X	X		
Alcohol-specific satiety questionnaire			X	X		
Drug Effects Questionnaire (DEQ)			X	X	X	
Visual Analogue Scale (VAS)			X	X		
Biphasic Alcohol Effects Scale (BAES)			X	X		
Subjective Effects of Alcohol Scale (SEAS)			X	X		
Alcohol Urge Questionnaire (AUQ)			X	X		
Alcohol Purchase Task (APT)			X	X		
Dot Probe task			X	X		
Breath Alcohol Concentration (BrAC)			X	X	X	
Transdermal Alcohol Concentration (TAC), measured via Skyn			X	X	X	
Ecological Momentary Assessment (EMA)					X	
DEXA scan					X	
Venipuncture blood sample x2			X	X		
Fingerprick blood sample x3			X	X		
Timeline followback (TLFB)						X
Brief young adult alcohol consequences questionnaire						X
Importance of consequences of drinking short-form						X
Return Skyn monitor						X

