naturalistic drinking contexts to assess the strength of the association between a novel TAC sensor (BACtrack Skyn) and breath alcohol (BrAC) measurements. In addition, we will also use a small non-intrusive light-based blood flow measurement device (placed on the participant's finger) and validate these measurements against the other metrics. These aims will be accomplished using data from two half-day visits to our lab at UNC campus, 1-2 days apart, followed by a 7-day remote assessment study and a final brief discharge visit (Figure 1). Lab visits involve a novel self-report questionnaire to assess alcohol-specific satiety during a paced alcohol challenge paradigm. In addition, on each of the two sessions in counterbalanced order, participants receive either a dietary supplement intended to stimulate postprandial GLP-1, or a calorically matched placebo to assess the effect of GLP-1 stimulation on alcohol-specific satiety. Two blood samples will be collected at each session to confirm plasma levels of glucagon-like peptide 1 (GLP-1). Blood fingerprick samples will be used to measure high-mobility group box 1 (HMGB1) inflammatory marker at three timepoints after alcohol administration. Additional measures of reward and incentive motivation for alcohol will be included to test the hypothesis that satiety is associated with reduced incentive motivation for alcohol reward. At the end of the second lab visit participants will be oriented to the 7-day remote assessment study. During the 7-day remote visit participants will be asked to wear the Skyn sensor continuously across 24-hours/day, except when bathing/showering or charging the device, and to initiate EMAs if they start an alcohol drinking bout. During drinking bouts, and for up to one hour following drinking bouts, participants will be prompted to record their BrAC every 20 minutes and to self-report the number of drinks consumed since the prior survey and subjective intoxication. Each morning, participants will complete daily diaries reporting alcohol-related harms experienced on the prior day. Following the 7-day remote visit, participants will complete a final discharge visit to return study devices, complete a timeline follow-back, and undergo a dual x-ray absorptiometry (DEXA) scan to assess fat-free mass, which will be included as a covariate in subsequent analyses to account for alcohol-elimination rate [56]..

[figure not shown]

Figure 1. Diagram of lab session procedures

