To analyze study aim 3, multi-level regression models will be used to assess within-person changes on repeated measures along with between-person individual differences. A linear growth curve model will be used to test the hypothesis that alcohol-specific satiety increases with time and additional drinks. Timepoint (1-6) and drug (alcohol or placebo) will be included in the model as within subject factors. Compared to placebo, alcohol is predicted to be associated with higher rates of change (slope) in satiety. Next, AUDIT will be included as a continuous predictor of slope in the model to test the hypothesis that participants with fewer alcohol dependence symptoms (lower AUDIT scores) report reduced satiety. Finally, subjective craving scores (Alcohol Urge Questionnaire; AUQ) from each timepoint will be included in the model. The effect of satiety over time is expected to remain significant after controlling for craving. Alcohol-specific satiety is expected to be negatively associated with measures of reward and incentive motivation for alcohol (BAES, APT, Dot Probe). Outcomes from each of these measures will be included in separate multi-level models with satiety scores as the primary dependent measure and timepoint (1-6) and drug (alcohol, placebo) as within-subject factors to determine the effect of additional dependent measures on within-person change in alcohol specific-satiety over time (slope).

To analyze aim 4, a repeated measures analysis of variance (ANOVA) will be used to assess the effect of a dietary supplement on alcohol-specific satiety in a 2(alcohol, placebo) x 2(timepoints) design. It is

predicted that compared to placebo, a GLP-1 stimulating dietary supplement will increase alcohol-specific satiety.

To analyze aim 5, linear regression will be used to assess the association between HMGB1 levels as a function of BrAC during the laboratory alcohol sessions. Data processing and analyses will be completed in R and SPSS.

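### Aim 3 control drinks are matched on volume but not on energy, and the planned analysis never sets alcohol-specific satiety against the hunger and fullness ratings it collects

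*Combined protocol and SAP*

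**What the plan says.** **Drinks (section 4.3).** The alcohol drinks are specified as follows: "Drinks will consist of 40 proof vodka and a sugar-free cranberry juice mixer at a 1:5 ratio". The control drinks are described differently: "Control drinks contain cranberry juice with an alcohol mask (rim sprayed with vodka) matched in total volume to the alcohol drinks". Sugar-free is not repeated for the control juice, and no energy matching is mentioned. The purpose given for the control session is expectancy: "The control session will control for expectations of increased satiety with subsequent drinks". Participants attend both lab visits after an overnight fast.

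**Priming drink (section 1.2).** The schedule row "Administer alcohol priming drink" is ticked for both lab visits.

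**Fullness ratings (sections 1.2 and 4.3).** Visual analogue scale (VAS) items for hunger, fullness and satiety are collected at both lab visits. Section 4.3 lists them after the priming drink. It then says that subjective response questionnaires are repeated after each drink, without saying whether the VAS items are among them.

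**Analysis (section 8.1, Aim 3).** A linear growth model has timepoint (1 to 6) and drug as within-subject factors. The key prediction is: "Compared to placebo, alcohol is predicted to be associated with higher rates of change (slope) in satiety". AUDIT and then craving (AUQ) are added, and separate models bring in BAES, the purchase task and the dot probe. The VAS appears in none of these models, nor among the Aim 3 measures in section 3.

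**The concern.** Aim 3 introduces a construct that sections 2.2 and 4.3 describe as new and previously unmodelled. A steeper satiety slope under alcohol is the result that would support it. If the two sessions also differ in energy intake, in people who have fasted overnight, ordinary fullness could contribute to the same slope difference.

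The timing makes this relevant. An energy difference present throughout a session would shift the level of satiety and leave the slope largely alone. A difference that grows with every drink lies along the drug-by-timepoint term itself. Adjusting for craving does not address it, because craving and fullness are different states. The documents report no evidence that the new questionnaire discriminates between alcohol satiety and fullness, so this study is the place to look. As planned, a fullness difference between sessions would go unexamined and could be reported as alcohol-specific satiety.

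**Working it through.** The documents state no energy figure, so there is none to reproduce. The check derives one from the stated drink volumes.

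**Inputs from section 4.3**
- Volume: "Average volume of a drink, alcohol+mixer at a 1:5 ratio is 8/5oz for a man/woman".
- Vodka of 40 proof, which is 20% ethanol by volume.
- Ratio 1:5, read as one part vodka to five parts mixer, so vodka is 1/6 of the drink.
- Five mini-drinks.

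**Assumptions not in the documents**
- 29.57 mL per fluid ounce and ethanol density 0.789 g/mL.
- 7 kcal per gram of ethanol (range 6.93 to 7.1).
- Sugar-free mixer counted as 0 kcal.

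**Step 1: ethanol per mini-drink** = ounces × 29.57 × 1/6 × 0.20 × 0.789
- Men: 8 × 29.57 × 1/6 × 0.20 × 0.789 = 6.22 g
- Women: 5 × 29.57 × 1/6 × 0.20 × 0.789 = 3.89 g

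**Step 2: energy** = grams × 7, then × 5 drinks
- Men: 43.6 kcal per drink, 218 kcal over five (216 to 221 across 6.93 to 7.1 kcal/g)
- Women: 27.2 kcal per drink, 136 kcal over five (135 to 138)

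If 1:5 means one part in five of the total, the results are 261 and 163 kcal.

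**Step 3: cross-check from the target rise of 10 mg% per drink.** By a Widmark calculation, with assumed distribution factors r of 0.68 (men) and 0.55 (women), grams over five drinks = 5 × r × kg × 0.1. A man of 80 kg gets 5 × 0.68 × 80 × 0.1 = 27.2 g, or 190 kcal. Men of 60 to 100 kg give 143 to 238 kcal, and women of 50 to 80 kg give 96 to 154 kcal. The volume-based figures fall within these ranges.

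**Step 4: dependence on the control juice.** Total control volume is 5 × 8 = 40 oz for men and 5 × 5 = 25 oz for women. The table keeps the alcohol mixer at 0 kcal.

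| Control juice, kcal per 8 oz (assumed) | Alcohol minus control, men | Alcohol minus control, women |
|---|---|---|
| 0 (same sugar-free mixer) | +218 | +136 |
| 10 | 218 − 50 = +168 | 136 − 31 = +105 |
| 50 | 218 − 250 = −32 | 136 − 156 = −20 |
| 110 | 218 − 550 = −332 | 136 − 344 = −208 |

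The sign changes at about 44 kcal per 8 oz (218 ÷ 5 for men; 136 ÷ 3.125 for women).

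**Step 5: alignment with the tested slope.** One priming drink plus five mini-drinks gives six drinks, which fits the six timepoints in section 8.1. On that reading, timepoint 1 follows the priming drink, which is the same at both visits. With the same sugar-free mixer, the cumulative gap at timepoints 1 to 6 is:
- Men: 0, 44, 87, 131, 174, 218 kcal
- Women: 0, 27, 54, 82, 109, 136 kcal

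The gap is linear in timepoint and zero at the start, which is the pattern a drug-by-timepoint slope picks up. With ordinary juice it would also build linearly but could run the other way, and could then mask a true alcohol effect.

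**The case against.** The case on the other side is substantial, and much of it stands.

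- **The energy excess is conditional.** A reader might infer that the alcohol session necessarily carries more energy. Section 4.3 does not say that the control juice is sugar-free. The same mixer is the natural reading, but the text supports only that energy is unmatched or unspecified.
- **Separation is possible.** A reader might infer that Aim 3 cannot tell alcohol satiety from fullness. That is too strong. Volume is already matched, the outcome is a questionnaire written for alcohol satiety, other alcohol-directed measures are modelled, and fullness ratings are collected. The gap is mainly a missing line in the analysis plan.
- **Ethanol's energy comes with ethanol.** The alcohol-versus-control contrast therefore remains a valid total effect. Alcohol-specific could also be read as naming the object of satiety, without excluding an energy route. This stands as far as the contrast goes, but the label still needs care.
- **No contradiction over calorie matching.** The phrase "or a calorically matched placebo to assess the effect of GLP-1 stimulation on alcohol-specific satiety" concerns the supplement placebo, used for Aim 4. The control drinks have a different stated purpose. The phrase shows that the protocol takes energy into account elsewhere, and no more.
- **No false-positive rate can be given.** It would need the effect of this energy on fullness, the questionnaire's sensitivity to fullness, and the variance of the slope difference. The documents give none of these.

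The objection does not remove the central point: nothing in the Aim 3 plan examines whether fullness follows the same drug-by-time course as the satiety score.

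**Conclusion.** The concern holds in a limited form. Control mini-drinks are matched on volume only, and their energy is unmatched or unspecified. If both sessions use the same sugar-free mixer, the alcohol session carries about 218 kcal (men) or 136 kcal (women) more over five drinks, assuming 7 kcal/g and the stated average volumes. The difference accumulates along the slope being tested. If the control juice is ordinary juice, the size and even the direction are unknown.

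The alcohol-versus-control comparison is not invalidated. What lacks support is the label: the plan tests satiety against craving and alcohol motivation but not against general fullness. It would also go too far to require the satiety slope to exceed the fullness slope on standardised scales before any claim is made. Such a rule depends on each scale's reliability, has low power, and could relabel a real alcohol effect whenever alcohol raises both.

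This is an inexpensive improvement to a pilot study's analysis. It does not settle a separate question: how the supplement and alcohol factors are allocated across the same two lab visits.

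**What to change.** **Section 4.3.** State whether the control juice is the same sugar-free mixer. State that the hunger, fullness and satiety VAS items are repeated with the questionnaires at timepoints 1 to 6.

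**Section 8.1, Aim 3.**
1. Fit the same timepoint-by-drug growth model to VAS fullness and VAS hunger as parallel outcomes. Report the slope differences, with confidence intervals, beside the satiety result.
2. Add a sensitivity model of satiety with fullness as a time-varying covariate, in the way already planned for AUQ. Note that fullness is measured after treatment and may lie on the pathway from alcohol to satiety, so the adjusted estimate does not replace the total effect.
3. Fix the wording of the conclusion in advance. If fullness shows a similar drug-by-time effect, or the satiety slope difference does not hold after adjustment, describe the finding as satiety that may include general fullness.

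**Cost.** A few VAS items at existing assessment points, if they are not already repeated there; one or two added models; and possibly a more cautious claim. The drinks and the sample size stay as they are.

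### As the text stands, the purchase task and dot probe have one timed post-alcohol reading, taken before the alcohol and control sessions diverge, yet section 8.1 enters them in six-timepoint satiety models by drug

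*Combined protocol and SAP*

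**What the plan says.** **Timing of the tasks.** Section 4.3 records that "Baseline measurements of study outcomes will be taken at this time" on arrival, without itemising the measures. After the supplement and second blood sample comes the prime: "Next, a priming drink (calculated to achieve 30mg% BAC) is administered to stimulate craving for alcohol". Then: "Fifteen minutes after the priming drink, a novel alcohol-specific satiety questionnaire will be administered followed by alcohol incentive motivation tasks", the two tasks named being the APT and the dot probe. The subjective response questionnaires (DEQ, BAES, AUQ, SEAS) follow as a separate item in the same list.

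**Paced drinking.** Five mini-drinks, alcohol or control, are given over two hours. What recurs is stated as "Subjective response questionnaires are repeated 15 minutes after each drink", plus breath alcohol every 15 minutes. The text then moves to the last fingerprick and recovery.

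**Dot probe description.** Later in section 4.3: "Attentional bias will be assessed before and after alcohol administration and change scores will be calculated". There is no equivalent sentence for the APT.

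**Schedule of Activities (section 1.2).** The row "Administer alcohol priming drink" is ticked at both study visits. The APT and dot probe rows are also ticked by visit, with no times within the visit. The list of measures in section 4.3 sends the reader to a section 1.3 for time points, but the contents page lists only 1.1 and 1.2.

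**Analysis (section 8.1, Aim 3).** Satiety is expected to be negatively related to the BAES, APT and dot probe. The plan is: "Outcomes from each of these measures will be included in separate multi-level models with satiety scores as the primary dependent measure and timepoint (1-6"), with drug as the second within-subject factor. The stated purpose is to see how these measures affect the within-person slope of satiety.

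**The concern.** The slope analysis asks whether incentive motivation moves with satiety as drinking proceeds, and drug is a factor in the model. To inform that question, a predictor needs values that change across the timepoints, or at least a value taken after the alcohol and control sessions have become different.

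The one timed post-alcohol reading of each task meets neither need. It falls at the first modelled timepoint, after a drink given to provoke craving, when both sessions have had the same alcohol. Satiety is predicted to build later, over the mini-drinks.

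If staff follow the text as written, the missing readings cannot be recovered at analysis. The analyst would have to leave five of six cells empty, carry the post-prime value across all six, or change the model after the data are in.

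**Working it through.** **1. The plan's own figure.** The only stated figure nearby is N = 42 for 86% power in section 8.2. It does not bear on task timing, and it cannot be pinned down because the number of groups, number of measurements and correlation are not given. The repeated-measures within-between formula is λ = f²Nm/(1−ρ), df1 = (k−1)(m−1), df2 = (N−k)(m−1), where k is the number of groups and m the number of measurements. With assumed f = 0.25 and ρ = 0.5:
- k = 2, m = 2: λ = 0.0625 × 42 × 2/0.5 = 10.5, power 0.885
- k = 3, m = 2: the same λ, power 0.803
- k = 6, m = 5: λ = 26.25, power 0.859

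The figure is neither confirmed nor refuted, and nothing below depends on it.

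**2. Mapping the timepoints.** One post-prime assessment plus five post-mini-drink assessments gives 1 + 5 = 6, which matches timepoints 1-6. This mapping is an inference, but no other count in the text gives six.

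**3. Counting values, by the text.**

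| Measure | Timed post-alcohol values per session | Per person (2 sessions) | At N = 42 |
|---|---|---|---|
| Satiety | 6 | 12 | 504 |
| APT | 1 | 2 | 84 |
| Dot probe | 1 | 2 | 84 |

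Each task therefore fills 84/504 = 1/6 of the cells. A baseline reading may exist as well, but it precedes all alcohol.

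**4. Are the tasks among the repeated questionnaires?** The synopsis lists questionnaires and tasks as separate classes and puts behavioral economic demand and attentional bias under tasks. Section 4.3 makes the same split in its list of post-prime measures, and it describes both measures under a behavioral-tasks heading. The sentence on repetition names questionnaires only.

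**5. Would repetition after every mini-drink fit?** Inputs from section 4.3: 3 minutes to drink, 15 minutes' absorption, APT no more than 5 minutes, dot probe 5 minutes, two hours in all.
- Without tasks: 5 × (3 + 15) = 90 min. This leaves 120 − 90 = 30 min, or 6 min per drink, for questionnaires and breath alcohol.
- With tasks after each absorption period: 5 × (3 + 15 + 10) = 140 min, which exceeds 120.
- Loosest serial count, in which only the fifth drink must finish inside two hours: 4 × 28 + 3 = 115 min. This leaves 5 minutes for four rounds of questionnaires.
- With tasks during absorption: 90 min, which fits.

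Repetition after every drink is thus implausible but not excluded by timing. It also sits badly with a single before/after change score for the dot probe.

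**6. Contrast at the one timed reading.** The prime targets 30 mg% in both sessions, so the designed difference in alcohol given is zero. The alcohol session then goes on to a stated maximum of 60-70 mg%. The further 30 to 40 mg% (60 − 30 to 70 − 30) has no scheduled task reading. By that point the supplement or its placebo has already been given, so a task difference between sessions at the post-prime reading could reflect the supplement, visit order or noise, but not the alcohol-control manipulation.

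**The case against.** The strongest reply is that much of this rests on silence. No sentence says the tasks are not repeated. Alcohol is given from the prime through to the fifth mini-drink, so the dot probe's reading after alcohol could be one taken after the last drink. Figure 1, the diagram of session procedures, might show exactly that. This stands: it is why the point is limited to the readable text. It does not settle the matter, because the sentence covers only the dot probe, does not say which reading is meant, and would still not supply six timepoints.

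A second reply is that satiety, not the task score, is the outcome over timepoints 1-6, and a single session-level score can legitimately predict a slope. Section 8.1 specifies scores from each timepoint for the AUQ but not for the APT or dot probe. This also stands: the model could be fitted. But the plan does not say that the scores enter at session level, and such a score would still predate any alcohol-control difference.

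A reader might go further and infer that the tasks are definitely given only at baseline and post-prime, or that the link between satiety and incentive motivation cannot be tested at all. The documents support neither. Both tasks directly follow the satiety questionnaire after the prime, so an association at timepoint 1 is estimable, though at low exposure. The BAES, named in the same hypothesis, is repeated after each drink.

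Finally, section 3 lists demand and attentional bias as secondary measures, and the study is a pilot. That limits the severity.

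**Conclusion.** The point holds in a limited form. On the readable text, the APT and dot probe each have one timed post-alcohol reading per session, at the first of six modelled timepoints, when the designed difference in alcohol between sessions is zero. As scheduled, they cannot serve as time-varying predictors of satiety slope, and they carry no alcohol-control contrast. The cross-sectional association at timepoint 1, the BAES and AUQ analyses, and the sample size are untouched.

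This rests on three assumptions: that Figure 1 does not show a later task reading, that timepoint 1 is the post-prime assessment, and that the tasks are not meant to be included in the repeated questionnaires. If Figure 1 does show a reading after the last drink, what remains is to write it into section 4.3 and bring section 8.1 into line. Severity is moderate. It is worth acting on because a reading that was not taken cannot be recovered later.

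**What to change.** **Section 4.3 and the Schedule of Activities.** State the within-visit times of both tasks. Unless Figure 1 already shows it, add one APT and one dot probe at both visits after the questionnaires for the fifth mini-drink. Fix their order relative to the final fingerprick, so that the timing of that sample is the same at both visits. Say which reading after alcohol the dot probe change score uses. Replace the section 1.3 pointer with a reference to a within-visit timetable.

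**Section 8.1.** For these two measures only, replace the six-timepoint predictor models with change from post-prime to post-final-drink, related to the change in satiety over the same interval. Include drug, supplement and visit order, because each session carries both manipulations; separating drug from supplement requires that their pairing varies between participants, which the plan should state. This gives two change scores per person, 84 at N = 42. Keep the six-timepoint models for the BAES and AUQ.

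**Cost.** About 5 + 5 = 10 minutes per visit, 20 per participant, with no new staff or equipment. Participants already stay until breath alcohol returns to zero, so little is added to the visit, though some may reach zero sooner at the control visit. One more repetition may bring a practice effect. It should be similar in both sessions, and visit order in the model helps to absorb any carry-over between visits.
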